NCT02361944

Protocol dated 4/7/2016

The Effect of Maintaining Physiologic Oxygenation on Oxidative Stress During Cardiac Surgery

The Risks of Oxygen during Cardiac Surgery (ROCS) trial

PI: [name] [name], MSCI

We will test the hypothesis that maintenance of physiologic oxygenation during cardiac surgery reduces oxidative stress and postoperative organ injury compared to the hyper-oxygenation. Markers of oxidative stress, including F₂-isoprostanes and isofurans, increase significantly during cardiac surgery and independently predict a 38% increase in the odds of postoperative kidney injury, a devastating complication of surgery.¹ F₂-isoprostanes are also increased during surgery in patients that develop new-onset atrial fibrillation and may be increased in patients that develop postoperative delirium and long-term cognitive dysfunction. The administration of high doses of oxygen increases the production of reactive oxygen species (ROS) *in vitro* and in rodents, and ROS chemically modify and damage DNA, other proteins, and lipids. Hyperoxia may induce organ injury during surgery.

Anesthesiologists have administered supplemental oxygen to avoid hypoxemia in patients for the last 60 years. The development and widespread use of continuous pulse oximetry hemoglobin oxygen saturation (SpO₂) monitors in the 1980's and point-of-care arterial blood gas measurement machines more recently have not affected the practice of administering excess supplemental oxygen during surgery. During cardiac surgery, for example, anesthesiologists typically ventilate patients with 100% oxygen. Ninety-nine percent of the oxygen transported in blood is bound to hemoglobin, and administering oxygen at concentrations higher than those needed to saturate hemoglobin does not significantly increase oxygen content in blood. It does however increase the partial pressure of oxygen in plasma to super-physiologic levels. These super-physiologic levels may increase the production of ROS² and increase oxidative stress and its deleterious consequences in surgical patients.

Not until recently have we realized that the administration of excess oxygen might be harmful to patients. Following cardiac arrest and successful cardiopulmonary resuscitation (CPR), for example, hyper-oxygenation is associated with worse neurologic recovery, coma, and a 44% increase in the odds of death per 100 mmHg change in partial pressure of oxygen (PaO₂).³ This hyperoxia-associated organ injury may be mediated by oxidative stress.⁴ We hypothesize that hyper-oxygenation, defined as the administration of oxygen concentrations greater than what is required to maintain arterial hemoglobin saturation, increases oxidative stress and renal dysfunction compared to maintenance of physiologic oxygenation during cardiac surgery. If we find that maintenance of physiologic oxygenation during cardiac surgery attenuates oxidative stress, we may be able to reduce the neurologic and renal morbidity associated with cardiac surgery worldwide.

Table of Contents:

Study Schema

- 1.0 Background**
- 2.0 Rationale and Specific Aims**
- 3.0 Animal Studies and Previous Human Studies**
- 4.0 Inclusion/Exclusion Criteria**
- 5.0 Enrollment/Randomization**
- 6.0 Study Procedures**
- 7.0 Risks of Investigational Agents/Devices (side effects)**
- 8.0 Reporting of Adverse Events or Unanticipated Problems involving Risk to Participants or Others**
- 9.0 Study Withdrawal/Discontinuation**
- 10.0 Statistical Analysis Plan**
- 11.0 Privacy/Confidentiality Issues**
- 12.0 Follow-up and Record Retention**
- 13.0 References**

1.0 Background

Mammals require oxygen for oxidative phosphorylation. Prolonged deprivation of oxygen (hypoxia) leads to organ injury and death. Anesthesiologists administer supplemental oxygen (fractions of inspired oxygen [FIO_2] > room air [21%]) to patients undergoing surgery to avoid hypoxia. In the majority of patients undergoing surgery, however, supplemental oxygen administration is not required to maintain hemoglobin oxygen SpO_2 , and with the development of continuous pulse oximetry, the excess administration of supplemental oxygen may not reduce the incidence of hypoxia. In addition, oxygen administration in excess of that required for oxidative phosphorylation may increase the production of ROS, leading to oxidative stress. Oxidative stress causes direct damage to proteins including DNA and lipids, resulting in organelle autophagy, cellular apoptosis and necrosis, organ injury and dysfunction, and death.

2.0 Rationale and Specific Aims

Acute kidney injury (AKI) is a devastating complication following cardiac surgery. Five hundred thousand people undergo cardiac surgery each year in the U.S.,⁵ and AKI complicates recovery in up to 30% of these patients, requiring renal replacement therapy (dialysis) in 1-4%.⁶⁻⁹ AKI is associated with postoperative arrhythmias, wound infections, and sepsis, and AKI independently predicts a 5-fold increase in death at 30 days.¹⁰⁻¹³ We have demonstrated that F_2 -isoprostanes, products of arachidonic acid peroxidation that have emerged as the gold standard for the measurement of oxidative stress *in vivo*,¹⁴ increase significantly *during* cardiac surgery and independently predict an increased incidence of AKI.¹ Isofurans are products of arachidonic acid peroxidation formed preferentially over F_2 -isoprostanes under conditions of increased oxygen tension,¹⁵ and we have found that isofurans increase to a greater extent than F_2 -isoprostanes during cardiac surgery and are associated with AKI.¹⁶ Hyperoxia increases production of ROS *in vitro* and in rodents,¹⁷ and in recent clinical studies hyper-oxygenation during resuscitation from cardiac arrest independently predicted persistent coma and death.^{3,4,18} In preliminary studies, we found that cardiac surgery patients are exposed to oxygen concentrations well above those required to maintain hemoglobin oxygen saturation (median arterial partial pressure of oxygen [PaO_2] = 364 mmHg during surgery) and reducing excess oxygen exposure reduces both F_2 -isoprostanes and isofurans. Moreover, reducing excess oxygen exposure was associated with less postoperative renal injury.

We hypothesize that physiologic oxygenation during surgery decreases the generation of reactive oxygen species, decreases oxidative damage, and decreases kidney dysfunction following cardiac surgery compared to hyper-oxygenation. To test this hypothesis we propose the following **SPECIFIC AIMS**:

Aim 1: Test the hypothesis that maintaining physiologic oxygenation during anesthesia for cardiac surgery decreases postoperative kidney injury.

We will recruit and randomize 200 cardiac surgery subjects to hyper-oxygenation ($\text{FIO}_2 = 0.8-1.0$, usual care) or physiologic oxygenation (minimum FIO_2 required to saturate arterial hemoglobin 95-97% and maintain a PaO_2 between 80-110 mmHg) during surgery. We will compare postoperative changes in serum creatinine and markers of nephron injury (neutrophil gelatinase-associated lipocalin [NGAL], between subjects randomized to physiologic oxygenation or hyper-oxygenation to test the hypothesis that maintaining physiologic oxygenation during anesthesia for cardiac surgery decreases postoperative kidney injury. To assess tissue oxygenation in the two study groups, we will continuously measure (automatically recorded every 5 seconds) the FIO_2 , SpO_2 , brain O_2 saturation, and muscle O_2 saturation. In addition, we will measure the PaO_2 , cardiac output, and arterial lactate prior to, during, and following surgery but no less frequently than every hour. We will compare these oxygenation metrics between subjects randomized to hyper-oxygenation vs. physiologic oxygenation to assess oxygen delivery and

consumption between groups. The primary endpoints of Aim 1 will be serum creatinine change (median +/- 95% confidence interval (CI)). Secondary endpoints include additional measures of AKI (incidence of AKI [defined using KDIGO criteria], neutrophil gelatinase-associated lipocalin [NGAL], and insulin-like growth factor-binding protein 7 [IGFBP7]/tissue inhibitor of metalloproteinases-2 [TIMP-2]), incidence of delirium (measured using CAM-ICU), duration of mechanical ventilation, duration of hospitalization, SpO₂ (median +/- 95% CI and area-under-the-curve (AUC) < 90%), PaO₂ (median +/- 95% CI, AUC > 150 mmHg, and AUC < 70 mmHg), brain and muscle O₂ saturation (median +/- 95% CI and AUC < 80% baseline), and the percent of FIO₂ titrations within protocol (protocol adherence). Safety endpoints will focus on any risk of hypoxia between study groups and will include postoperative serum CK-MB measurements and rates of arrhythmias, reintubation, transient ischemic attack, stroke, and death.

Aim 2: Test the hypothesis that physiologic oxygenation during cardiac surgery reduces the generation of superoxide (measured by electron paramagnetic resonance of CAT-1H and TMH electron spin probes) and systemic oxidative stress (measured by plasma concentrations of F₂-isoprostanes and isofurans).

In subjects studied in the RCT described in Aim 1, we will measure plasma concentrations of F₂-isoprostanes and isofurans sampled prior to anesthetic induction, 30 minutes after initiation of cardiopulmonary bypass or OpCAB grafting, immediately following separation from cardiopulmonary bypass, at ICU admission, 6-hours after ICU admission, and on postoperative days 1 and 2. We will measure superoxide production in whole blood collected prior to anesthetic induction, immediately following separation from cardiopulmonary bypass, and on postoperative day 1. We will compare these measurements of ROS and systemic markers of oxidative stress between subjects randomized to physiologic oxygenation or hyper-oxygenation during surgery to test the direct effect of excess oxygen exposure on oxidative stress during surgery. By comparing these data to measurements of kidney function will also test a putative but unproven mechanism of surgery-induced AKI.

By accomplishing these 2 Aims we will improve our understanding of the mechanisms of perioperative oxidative stress and postoperative morbidity while assessing any damage of hyper-oxygenation during cardiac surgery. If we determine that hyper-oxygenation increases oxidative stress and/or organ injury, subsequent multicenter studies in cardiac and non-cardiac surgery patients will be performed to validate these findings. Ultimately, we could impact the perioperative management of 30 million annual surgical patients, since the vast majority of patients are hyper-oxygenated during surgery.

Effects on Endothelial Function Sub-study

Hyperoxia also induces vasoconstriction,¹⁹⁻²⁰ and ROS impair endothelial function.²¹ For example, pigs exposed to hyperoxia produced less endothelial-derived NO and had increased vasoconstriction compared to controls, and in humans hyperoxia-induced vasoconstriction is prevented by antioxidant treatment, indicating that the vasoconstriction effect of hyperoxia is at least partially mediated by ROS.²²⁻²³ These effects impair tissue perfusion and may be integral to development of postoperative organ injury. Therefore, endothelial function secondary to hyperoxia, secondary to oxidative stress, or independent from oxidative stress may be an important contributor to kidney, brain, and heart injury following cardiac surgery. The ROCS trial provides an ideal framework to test these hypotheses based on the ROCS trial population for the study, randomized oxygen treatments, detailed hemodynamic, perfusion, and oxygenation characterization, blood and tissue sampling, and outcomes assessments.

To test the hypotheses that physiologic oxygenation during cardiac surgery improves endothelial function compared to hyper-oxygenation (sub-study Aim 1), that endothelial dysfunction correlates with oxidative stress in patients having cardiac surgery (sub-study Aim 2), and that perioperative endothelial dysfunction is associated with organ injury (sub-study Aim 3) we will measure endothelial function at baseline (pre-intervention) and following cardiac surgery and compare these measurements between randomized oxygenation groups and to the ROS, F₂-isoprostanate/isofuran, oxygenation, and outcomes data generated in the ROCS trial. We will assess endothelial function at baseline and following surgery by quantifying brachial artery flow mediated dilation (FMD), performing peripheral arterial tonometry to

determine reactive hyperemia index, measuring endothelium-dependent and independent vasodilation in epicardial fat arterioles and distal mammary artery segments *ex vivo* using wire myography, and measuring markers of endothelial activation (E-selectin and plasminogen activator inhibitor [PAI]-1) in blood.

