6.0 Study Procedures

We will study 200 adult cardiac surgery patients and randomize them to either hyper-oxygenation during or physiologic oxygenation during cardiac surgery.

Once we have obtained informed consent, we will collect baseline data from the medical record. Upon arrival in the operating room, subjects will be placed on American Society of Anesthesiologists universal monitors as per standard care.

Oxygen administration and monitoring during and following surgery:

1. Hyper-oxygenation control group (usual care):

- Subjects will be preoxygenated with 100% FIO₂ prior to induction of anesthesia.
- Following induction of anesthesia and verification of tracheal intubation and lung ventilation, subjects will be ventilated with 100% oxygen with a tidal volume of 8 ml/kg ideal body weight, respiratory rate titrated to an end-tidal partial pressure of CO₂ of 35 cm H₂O, and positive end-expiratory pressure of 5 mmHg.
- During cardiopulmonary bypass, the oxygenator in the cardiopulmonary bypass circuit will be ventilated with 80% oxygen and gas flow titrated to achieve an arterial blood partial pressure of CO₂ of 50 mmHg. FIO₂ during cardiopulmonary bypass may be increased (see "Titration of FIO₂ during surgery" below).
- During transport from the operating room to the intensive care unit (ICU) following surgery, subjects will be connected to an Ambu bag and mechanically ventilated with 6 liters oxygen per minute fresh gas flow.
- Upon arrival in the ICU, subjects will be placed on the ICU ventilator and ventilated with 40% oxygen with a tidal volume of 8 ml/kg of ideal body weight, respiratory rate of 12 breaths per minute, and positive end-expiratory pressure of 8 mmHg, as is usual practice.
- Subsequent mechanical ventilation, supplemental oxygen administration, and subject extubation will be at the discretion of the ICU intensivist.

2. Physiologic oxygenation group:

- Subjects will be preoxygenated with 100% FIO₂ prior to induction of anesthesia (similar to hyper-oxygenated group subjects).

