The DSMB will receive report on the progress, adverse events, safety endpoints, and clinical outcomes at each interim analysis from the PI and the statistician. The first planned interim analyses will occur after 20 (11.1%) subjects have been studied and discharged from the hospital following surgery. At this meeting, the DSMB will evaluate subject recruitment, the documentation of subject data, and the collection and reporting of adverse events, serious adverse events, and safety endpoints. The DSMB will also evaluate any study withdrawals, any adverse events, in-hospital all-cause mortality, and safety outcomes (stroke, TIA, or Q-wave myocardial infarction).

The second planned interim analyses will occur after 100 (50%) subjects have been studied and discharged from the hospital following surgery. At this meeting, the DSMB will evaluate any study withdrawals, any adverse events, in-hospital all-cause mortality, safety outcomes (stroke, TIA, or Q-wave myocardial infarction), and a conditional power analysis implemented by the study statistician. The conditional power analysis will assess the likelihood of rejecting the null hypotheses (for the primary endpoints of Aims 1 and 2) at the study conclusion (N=200), assuming that the effect of intervention is as large or larger than the estimated effect at the second interim analysis (N=100). To do so, the study statistician will compare mock-unblinded data (A vs. B, where it remains unknown if A or B is normoxia or

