10.0 Statistical Analysis Plan

The primary objective of the analysis will be to compare the effect of intraoperative oxygenation on oxidative damage and organ injury. The primary endpoint of Aim 1 will be change in serum creatinine from baseline (defined as the most recent creatinine measured prior to surgery) to postoperative day 2. The primary endpoint of Aim 2 will be F₂-isoprostanes/isofurans measured in plasma.

Sample Size Calculations

We calculated the subject sample size based on data from the Vanderbilt Statin AKI Cardiac Surgery RCT (PI: [name]).²⁷ Data from this study indicate that mean serum creatinine concentrations increase 0.08 ± 0.37 mg/dl from baseline to postoperative day 2. We have powered the present randomized clinical trial conservatively, particularly since consensus criteria for AKI diagnosis define AKI as a 0.3 mg/dl rise in serum creatinine from baseline to postoperative day 2.²⁹ With 200 subjects, we will have 80% power to detect a 0.15 ± 0.375 mg/dl difference in serum creatinine between groups, with a type I error rate of 5%. In addition, with 200 subjects we will have 80% power to detect a 20 ± 50 pg/ml difference in plasma F₂-isoprostanes between groups, and we observed that physiologic oxygenation was associated with 35 ± 30 pg/ml less increase in plasma concentrations of F₂-isoprostanes among pilot subjects compared to hyper-oxygenated subjects. To account for a potential dropout rate of 10%, we plan to recruit 222 subjects.

For the endothelial function sub-study, we calculated the sample size based on a prior study of patients administered an oral antioxidant, treatment improved FMD 2.3% more than placebo with a standard deviation of 2.0%.³⁰ With 80 patients, we will have greater than 80% power to detect a 2%

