Every effort will be made to avoid missing data. Any methods of missing data imputation (e.g. multiple imputation using the chained-equations method) will be used cautiously as sensitivity analyses; and the analysis of results with imputation would be interpreted in the context of corroboration with the analyses without imputation. The primary analysis will be intention-to-treat. Before data unblinding, [name] will examine any protocol deviations and identify a list of protocol violators. In addition to the intention-to-treat analysis, a secondary per-protocol analysis will be conducted.

Specific inferences on the effects of interest will be made by reporting point estimates, along with 95% confidence intervals. Hypotheses will be tested at a two-sided significance level of $\alpha=0.05$. This data analysis plan will be carried out using the statistical analysis package R (R Development Core Team).

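### Sections 2.0 and 6.0 randomise 200 patients, but Section 10.0 treats 200 as the number left after 10% dropout and recruits 222; the plan does not reconcile the two

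*Combined protocol and SAP*

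**What the plan says.** Section 2.0 (Aim 1) states: "We will recruit and randomize 200 cardiac surgery subjects". Section 6.0 opens in the same way: "We will study 200 adult cardiac surgery patients and randomize them".

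Section 10.0 (Sample Size Calculations) gives the power for the Aim 1 primary endpoint: "With 200 subjects, we will have 80% power to detect a 0.15 ± 0.375 mg/dl difference in serum creatinine between groups". For Aim 2 it says that "with 200 subjects we will have 80% power to detect a 20 ± 50 pg/ml difference in plasma" F₂-isoprostanes. It then adds: "To account for a potential dropout rate of 10%, we plan to recruit 222 subjects".

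Section 6.0 (Data and Safety Monitoring Board) says: "The first planned interim analyses will occur after 20 (11.1%) subjects" have been studied and discharged. The next paragraph labels the second look, at 100 patients, as 50% and gives N=200 at the end of the study. The sub-study text in Section 10.0 also describes the full cohort as 200 patients.

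**The concern.** Section 2.0 applies both recruitment and randomisation to 200 patients, while Section 10.0 recruits 222 so that 200 remain after losses. The figure of 200 is thus a number before dropout in one place and a number after dropout in the other. Power is only just above 80% at 200 evaluable patients, so there is almost no margin. If randomisation is closed at 200 on the strength of Sections 2.0 and 6.0, the allowance of 22 patients is not used and any later loss takes power below the target.

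The same ambiguity reaches the conditional power analysis at the second look. It projects to N=200 and compares the result with 80%, so the statistician needs to know whether that 200 is randomised or evaluable.

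**Working it through.** **Inputs**

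- Aim 1: difference 0.15 mg/dl, SD 0.375 (Section 10.0). Standardised difference d = 0.15/0.375 = 0.40.
- Aim 2: difference 20 pg/ml, SD 50 (Section 10.0). d = 20/50 = 0.40, so the same figures apply.
- Type I error 5% (Section 10.0, sample size), two-sided (Section 10.0, end of the analysis plan).
- Dropout 10% (Section 10.0).
- Allocation 1:1. This is an assumption: it is not stated outright, but two arms in blocks of two or four imply it.

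**Step 1: reproduce the plan's power.** With n per arm, the normal approximation is power = Φ(d·√(n/2) − 1.96).

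- n = 100: 0.40 × √50 = 2.828; 2.828 − 1.96 = 0.868; Φ = 80.7%.
- The t-test version gives 80.4%.

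The stated 80% with 200 subjects reproduces.

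**Step 2: reproduce the recruitment figure.** 200/(1 − 0.10) = 222.2, stated as 222. In reverse, 222 × 0.90 = 199.8, and t-test power at 99.9 per arm is 80.3%. So the 200 in Section 10.0 is the number after dropout.

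**Step 3: randomise 200 and lose 10% afterwards.** 200 × 0.90 = 180, or 90 per arm.

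- Normal approximation: 0.40 × √45 = 2.683; 2.683 − 1.96 = 0.723; Φ = 76.5%.
- t-test: 76.1%.

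**Step 4: allow for the planned Wilcoxon test (Aim 1).** The plan gives no efficiency figure. Assuming normal data and a relative efficiency of 0.955, the per-arm number is multiplied by 0.955 and the t-test power recomputed.

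| Evaluable | Per arm | t-test | Wilcoxon (assumed 0.955) |
|---|---|---|---|
| 200 | 100 | 80.4% | 78.5% |
| 180 | 90 | 76.1% | 74.1% |

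The like-for-like loss is about 4 percentage points in either column.

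**Step 5: check the interim labels.**

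- First look: 20/200 = 10.0%; 20/222 = 9.0%; 20/180 = 11.1%.
- Second look: 100/200 = 50%; 100/180 = 55.6%.

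The label 11.1% matches neither 200 nor 222. The label 50% matches 200.

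**The case against.** The strongest reply is that Section 10.0 is the dedicated sample-size section, that its arithmetic is right, and that it already covers the loss. It says 222 are recruited, not that 222 are randomised. If dropout means losses between consent and randomisation, then 222 recruited and 200 randomised could both be true, with power at 80.4%. Randomisation is also run centrally by the study statistician, and the text describes one institution, so no separate sites would act on Sections 2.0 and 6.0 alone. The conditional power review at 100 patients could also lead to a larger sample.

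Much of this stands. The calculation is correct, and 76% is a conditional figure. But the pre-randomisation reading is not written anywhere. Section 2.0 recruits as well as randomises 200, so even the recruitment figures differ. Section 9.0 foresees patients who withdraw after study oxygen has begun, and so after randomisation. The review at 100 patients is only a partial safeguard, because any increase depends on feasibility, funding and IRB approval.

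A reader might infer from the 11.1% that the monitoring schedule was built on 180 evaluable patients. The documents do not support this. No section states 180, the adjacent look uses 50% and N=200, and the sub-study text treats 200 as the completed cohort.

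**Conclusion.** The inconsistency is real and should be corrected. The number randomised is 200 in two sections, while the sample-size section needs 200 after dropout and recruits 222. Nothing in the plan links these figures or says when dropout occurs.

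With 200 randomised, t-test power lies between 80.4% (no later loss) and about 76% (the full 10% lost afterwards). On the assumed Wilcoxon efficiency the range is about 78.5% to about 74%. These figures assume 1:1 allocation and the plan's own standardised difference of 0.40. For Aim 2 they describe the plan's simple two-group calculation, not the power of the repeated-measures mixed model that will be used.

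A reader might conclude that the trial as planned has 76% power and that the stated 80% is wrong. That goes too far. The plan claims 80% for 200 subjects, which is correct, and the shortfall arises only if randomisation stops at 200 and the full 10% is lost afterwards.

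The 11.1% label is a separate clerical error. It does not affect type I error, because the looks allow no stopping for efficacy or futility.

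**What to change.** 1. State one number randomised and one number evaluable, and use them in Sections 2.0, 6.0 and 10.0. Say whether the 10% dropout falls before or after randomisation.
2. If dropout is after randomisation, 222 randomised for 200 evaluable matches Section 10.0.
3. If only 200 will be randomised and dropout follows, restate power as about 76% by t-test for both primary-endpoint calculations.
4. If 222 was meant as the number consented and 200 as the number randomised, say so, and state what loss after randomisation is expected.
5. Change the first interim label from 11.1% to 10%, in line with the 50% and N=200 that follow it.

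The cost is almost nothing. The 222 is already the planned recruitment, so items 1, 2 and 5 are changes of wording if dropout is after randomisation. The sponsor must settle which reading was intended, because randomising 222 would change the plan if dropout was meant to come before randomisation.
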